5.2.6.1.7 Suicidality assessment

Suicidality assessment to further evaluate the psychological status of the subject will be performed at the time points indicated in the [Flow Chart](#) using the Columbia Suicidal Severity Rating scale (C-SSRS).

The C-SSRS is a semi-structured, investigator-rated interview, developed by clinical experts in cooperation with the FDA, assessing both suicidal behavior and suicidal ideation. It does not give a global score, but provides some categorical and some severity information specifically for behavior and ideation.

The C-SSRS interview may be administered by any type of physician, psychologist, clinical social worker, mental health counselor, nurse, or coordinator with C-SSRS training. It has a typical duration of five minutes, and causes only a low burden on subjects. At a minimum, the interview consists of 2 screening questions related to suicidal ideation and 4 related to suicidal behavior, and may be expanded to up to 17 items in case of positive responses. Free text entries are allowed for; the investigator has to directly evaluate the scale and write a report.

The C-SSRS has been widely used in large multinational clinical trials. The C-SSRS will be administered at the screening visit (using the 'screening/baseline' version) with the aim to exclude subjects with active moderate or severe symptomatology within a specified time

Proprietary confidential information © 2021 Boehringer Ingelheim International GmbH or one or more of its affiliated companies

prior to the screening or baseline visit. The life time history of suicidal ideation and behavior will also be recorded.

After the baseline visit the assessment ‘since last visit’ will be performed at each clinic or phone visit (‘since last visit’ version). The investigator is to review positive and negative reports for plausibility and clinical relevance. Doubtful reports may be repeated or reports may be validated by a consulting psychiatrist. If there is a confirmed positive report of suicidal behavior or suicidal ideation type 4 or 5 after start of trial, the investigator is to immediately interview the subject during the clinic visit, and/or is to consult a psychiatrist. If the positive report is confirmed, appropriate actions for the subject’s safety have to be initiated.

All C-SSRS reports of suicidal ideation type 4 or 5 and all reports of suicidal behavior must be reported as separate SAEs by the investigator. For ‘Self-injurious behavior, no suicidal intent’ (Type 11) standard AE / SAE reporting rules are to be applied.

For each negative report (suicidal ideation type 1, 2 or 3) after start of the trial, the investigator is to decide based on clinical judgment whether it represents an adverse event (AE) as defined in the protocol, and if it is considered an AE then it must be reported accordingly.

5.2.6.2 Adverse event collection and reporting

5.2.6.2.1 AE collection

Upon enrolment into a trial, the subject’s baseline condition is assessed (for instance, by documentation of medical history/concomitant diagnoses), and relevant changes from baseline are noted subsequently.

Subjects will be required to report spontaneously any AEs as well as the time of onset, end time, and intensity of these events. In addition, each subject will be regularly assessed by the medical staff throughout the clinical trial and whenever the investigator deems necessary. As a minimum, subjects will be questioned for AEs (and concomitant therapies) at the time points indicated in the [Flow Chart](#). Assessment will be made using non-specific questions such as ‘How do you feel?’. Specific questions will be asked wherever necessary in order to more precisely describe an AE.

A carefully written record of all AEs shall be kept by the investigator in charge of the trial. Records of AEs shall include data on the time of onset, end time, intensity of the event, and any treatment or action required for the event and its outcome.

The following must be collected and documented on the appropriate CRF(s) by the investigator:

- From signing the informed consent onwards until an individual subject’s end of trial:
 - All AEs (serious and non-serious) and all AESIs
 - The only exception to this rule are AEs (serious and non-serious) and AESIs in Phase I trials in healthy volunteers, when subjects discontinue from the trial due to screening failures prior to administration of any trial medication or ketamine.

Proprietary confidential information © 2021 Boehringer Ingelheim International GmbH or one or more of its affiliated companies

In these cases, the subjects' data must be collected at trial site but will not be entered in the CRF or trial database and will not be reported in the CTR.

- After the individual subject's end of trial:
 - The investigator does not need to actively monitor the subject for AEs but should only report any occurrence of cancer and related SAEs and related AESIs of which the investigator may become aware of by any means of communication, e.g. phone call. Those AEs should, however, not be reported in the CRF.

5.2.6.2.2 AE reporting to the sponsor and timelines

The Investigator must report SAEs, AESIs, and non-serious AEs which are relevant for the reported SAE or AESI, on the BI SAE form immediately (within 24 hours) to the sponsor's unique entry point (country specific reporting process will be provided in the ISF). The same timeline applies if follow-up information becomes available. In specific occasions the Investigator could inform the sponsor upfront via telephone. This does not replace the requirement to complete and send the BI SAE form.

[figure not shown]
[figure not shown]
With receipt of any further information to these events, a follow-up SAE form has to be provided. For follow-up information, the same rules and timeline apply as for initial information.

5.2.6.2.3 Information required

All (S)AEs, including those persisting after the individual subject's end of trial, must be followed up until they have resolved, have been sufficiently assessed as 'chronic' or 'stable', or no further information can be obtained.

Proprietary confidential information © 2021 Boehringer Ingelheim International GmbH or one or more of its affiliated companies

Proprietary confidential information © 2021 Boehringer Ingelheim International GmbH or one or more of its affiliated companies

5.4 ASSESSMENT OF BIOMARKERS

5.4.1 Cambridge Neuropsychological Test Automated Battery (CANTAB)

Attenuation of [REDACTED] will be evaluated on the CANTAB test battery. The [REDACTED] assessed in this battery include: Paired Associates Learning task (PAL; visuospatial episodic memory), Spatial Working Memory (SWM; working memory), and Rapid Visual Information Processing (RVP; sustained attention).

The CANTAB tests will be performed in the same order, i.e. RVP, SWM, PAL, with a 4 min break between tests, pre-ketamine and during ketamine infusion, following administration of BI 409306 (T2) or BI 425809 (T3) or lamotrigine (T1, positive control) or placebo (R). The anticipated effects on the CANTAB tests on ketamine of the lamotrigine treatment (T1) will serve as a benchmark to conclude about effects on the CANTAB tests on ketamine of the BI 409306 (T2) or BI 425809 (T3) treatment. The use of placebo treatment (R) will allow estimating the impact of individual factors on the cognitive effects of the ketamine challenge.

The full list of outcome measures to be analysed from the CANTAB test battery is included in Table [5.4.1: 1](#) below.

The CANTAB tests (RVP, SWM, PAL) can be completed in approx. 35 minutes.

Table 5.4.1: 1

CANTAB tests, domains and outcome measures

CANTAB test	Domain	Outcome measurements
Paired Associates Learning (PAL)	Episodic memory & new learning	KEY: Total Errors Adjusted (PALTEA28) [REDACTED] [REDACTED]
Spatial Working Memory (SWM)	Executive function & working memory	KEY: Between Errors (SWMBE468) [REDACTED] [REDACTED] [REDACTED]
Rapid Visual Information Processing (RVP)	Sustained attention/vigilance	KEY: A Prime (RVPA)

5.4.1.1 Paired Associates Learning (PAL)

PAL assesses visual memory and new learning. [REDACTED]

Description: Boxes are displayed on the screen and open in turn to reveal a number of patterns. Participants are instructed to try to remember the location in which each pattern was shown. After all the boxes have been opened, each pattern is then shown in the center of the screen in a randomised order, and the participant touches the box in which the pattern was located. If an error is made, all the patterns are re-presented to remind the participant of their locations. As the test progresses so the stages become more difficult as the number of patterns to be remembered increases. For participants who fail to complete all levels, an adjusted total is calculated that allows for errors predicted in the stages that were not attempted.

Key Outcome Measure: Total Errors Adjusted (PALTEA28). The number of errors committed by the subject plus an adjustment for the estimated number of errors they would have made on any stages that were not reached. Calculated across all assessed two, four, six and eight box trials.

5.4.1.2 Spatial Working Memory (SWM)

SWM assesses the ability of the participant to retain spatial information and manipulate it in working memory. It is a self-ordered task that also gives a measure of strategy (an aspect of executive function). [REDACTED]

Description: A number of coloured boxes are presented on the screen, and the computer hides a token in these boxes one at a time. The participant is instructed to touch the boxes in turn to search for the token that has been hidden. When a token is found it should be placed in a home area on the right side of the screen. The participant then searches for more tokens

Proprietary confidential information © 2021 Boehringer Ingelheim International GmbH or one or more of its affiliated companies

until the same number of tokens as the number of coloured boxes has been found. The key task instruction is that the computer will never hide a token in the same coloured box twice in the same problem. As the test progresses, so it becomes more difficult.

[figure not shown]
Key Outcome Measure: Between Errors (SWMBE468). The number of times the subject incorrectly revisits a box in which a token has previously been found. Calculated across all assessed four, six and eight token trials.

5.4.1.3 Rapid Visual Information Processing (RVP)

[figure not shown]
RVP is a sensitive measure of sustained attention, outputting measures of response accuracy, target sensitivity and reaction times. [REDACTED]

Description: During the RVP task, single digits appear in a pseudo-random order at a rate of 100 digits per minute in a box in the centre of the screen. Subjects must detect a series of 3-digit target sequences (e.g. 3-5-7; 2-4-6; 4-6-8) and respond by touching the button at the bottom of the screen when they see the final number of the sequence. Nine target sequences appear every minute.

Key Outcome Measure: A' Prime (RVPA). The signal detection measure of a subject's sensitivity to the target sequence (string of three numbers), regardless of response tendency (the expected range is 0.00 to 1.00; bad to good). In essence, this metric is a measure of how good the subject is at detecting target sequences.

Proprietary confidential information © 2021 Boehringer Ingelheim International GmbH or one or more of its affiliated companies

5.5 BIOBANKING

Not applicable.

5.7 APPROPRIATENESS OF MEASUREMENTS

All measurements performed during this trial are standard measurements and will be performed in order to monitor subjects' safety and to determine pharmacokinetic and pharmacodynamic parameters in an appropriate way. The scheduled measurements will allow monitoring of changes in vital signs, standard laboratory values, C-SSRS, safety tests, and ECG parameters that might occur as a result of administration of trial medication. The safety assessments are standard, are accepted for evaluation of safety and tolerability of an orally and intravenously administered drugs, and are widely used in clinical trials. The pharmacokinetic parameters and measurements outlined in Section [5.3](#) are generally used assessments of drug exposure. The biomarkers and pharmacodynamic parameters and measurements outlined in Sections [5.4](#) and [5.6](#) are of exploratory nature only. The C-SSRS is a validated tool to monitor for suicidality and recommended by the FDA [[R12-4395](#)]. The visual acuity test is commonly used to screen for visual disturbances and can be extended to a full ophthalmologic examination if needed. DSST, MOAA/S, CADSS and SFST are commonly used for assessment and confirmation of subjects' fitness after administration of ketamine before discharge from the clinic. Recovery from ketamine will be evaluated as per criteria common in clinical practice.

6. INVESTIGATIONAL PLAN

6.1 VISIT SCHEDULE

Exact times of measurements will be documented. The acceptable time windows for screening and the end of trial examination are provided in the [Flow Chart](#).

Study measurements and assessments scheduled to occur ‘before’ planned time 0:00 on Day -21 to -2 of Visit 2 are to be performed and completed within a 2 h period prior to planned time 0:00.

Study measurements and assessments scheduled to occur ‘before’ trial medication administration on Day 1 of Visit 3, 4 and 5 are to be performed and completed within a 2 h period prior to the trial drug administration.

The acceptable deviation from the scheduled time for **C-SSRS assessments, targeted physical examination, safety tests (DSST, MOAA/S, CADSS and SFST) and laboratory tests** will be ± 2 h for all days.

On treatment days (Day 1 of Visit 3, 4 and 5) and at the Screening Ketamine Challenge (Day -21 to -2 of Visit 2), the planned times for **CANTAB tests, E** [REDACTED] as per the [Flow Chart](#) should be adhered as closely as possible *before ketamine infusion*, whereas *during ketamine infusion* time intervals between these tests should be minimized, i.e. if any test is completed earlier or dropped out, the next test should start straight away. Overall, deviations ± 15 min from the planned times for these tests are acceptable.

CANTAB tests, [REDACTED] at the Screening Ketamine Challenge (Visit 2) have to occur time-matched to these assessments in each treatment period (Visit 3, 4 and 5). Therefore, planned time 0:00 on Day -21 to -2, the Screening Ketamine Challenge, should equal planned time 0:00 relative to drug administration on Day 1 of Period 1, 2 and 3.

Before start of ketamine infusion and after confirmation of recovery from ketamine, the acceptable deviation from the scheduled time for **vital signs, ECG and Questioning for AEs and concomitant therapy** will be ± 15 min. *During ketamine infusion until confirmation of recovery from ketamine*, the planned times for vital signs, ECG assessments and Questioning for AEs and concomitant therapy as per the [Flow Chart C](#) and [Flow Chart D](#) should be adhered as closely as possible.

Ketamine infusion can be prolonged for a maximum of 15 min, i.e. to 105 min in total, in case delays from the planned time occur for CANTAB tests, [REDACTED] [REDACTED] Ketamine infusion is to be terminated earlier, if the above assessments on ketamine are completed (or any test drops out) [REDACTED] Evaluation as per **criteria of recovery from ketamine** must be not earlier than 60 min after stop of ketamine infusion.

If several actions are indicated in the [Flow Chart](#) at the same time point, the intake of meals will be the last action, and 12-lead ECG recordings have to be done first. Furthermore, if

Proprietary confidential information © 2021 Boehringer Ingelheim International GmbH or one or more of its affiliated companies

several measurements including venepuncture are scheduled for the same time, venepuncture should be the last of the measurements due to its inconvenience to the subject and possible influence on physiological parameters.

If a subject misses an appointment, it will be rescheduled if possible. The relevance of measurements outside the permitted time windows will be assessed no later than at the Report Planning Meeting.

[figure not shown]
6.2 DETAILS OF TRIAL PROCEDURES AT SELECTED VISITS

6.2.1 Screening period

After having been informed about the trial, all subjects will provide written informed consent in accordance with GCP and local legislation prior to enrolment in the study.

The screening period consists of the Screening Examination (Visit 1) and (if applicable) the Screening Ketamine Challenge (Visit 2). Only subjects who have already passed all eligibility criteria, incl. confirmation on CYP2C19 status, except not yet determined response to ketamine, will be invited to the Screening Ketamine Challenge, that has to be scheduled on a different day after the screening examination.

At the Screening Examination, genotyping for CYP2C19 will be performed in those volunteers whose genotypes have not been previously determined (for details, see Section [3.3.3](#) and [5.6.1](#)).

At the Screening Examination, subjects who are not able to tolerate procedures of  or demonstrate abnormal results will be excluded from further screening activities (see Section [5.2.5.3](#)).

At the Screening Examination (Visit 1) and the Screening Ketamine Challenge (Visit 2) prior to ketamine infusion, subjects will be tested on CANTAB RVP, SWM and PAL. Each subject will be compared to an age matched sample of normative individuals from Cambridge Cognition's CANTAB normative database (to be made for PALTEA28 only). Subjects will be excluded if they perform at any visit outside of the normative range (± 2 SD or percentile equivalent) for their age level on the PAL outcome measure PAL Total Errors Adjusted (PALTEA28). An indication of whether the subject should be excluded from further screening procedures due to absence of normative performance will be provided through the CANTAB software as a downloadable report and will be available after completion of the CANTAB assessments.

For the Screening Ketamine Challenge eligible subjects will come to the clinic in the morning of the test day, where they will participate in two assessment-sessions:

- Screening Baseline (= SCR BL)

CANTAB tests,  will be done without any treatment, i.e. with no ketamine infusion

Proprietary confidential information © 2021 Boehringer Ingelheim International GmbH or one or more of its affiliated companies

- Screening Ketamine (= SCR KET)

CANTAB tests, [REDACTED] will be done during ketamine infusion

SCR BL will be done first followed by SCR KET, as indicated in the [Flow Chart](#). Only subjects that show [REDACTED] will be allowed to enter the trial.

[REDACTED]. A change of 10 or more errors on PALTEA28 is equivalent to a 1 SD (between subjects) change in performance. This will allow ample variability to evaluate attenuation of k [REDACTED] between treatment arms. An indication of whether a participant should be screened out due to absence of [REDACTED] will be provided through the CANTAB software as a downloadable report and will be available following completion of the CANTAB assessments.

The assessments of SCR KET will also be used as baseline for the assessments performed on the test days of the treatment periods, i.e. under treatments T1, T2, T3 and R. Therefore, it is of upmost importance that SCR KET assessments will be performed time-matched, i.e. exactly at the same time of the day, to the later assessments under treatments T1, T2, T3 and R.

Recovery from ketamine must be confirmed via criteria of recovery from ketamine. Recovery follow up can be terminated after a minimum of 60 minutes when all applicable recovery criteria are met (see Section [5.2.5.6](#)).

During and after assessments subjects are kept under close medical surveillance for at least 5 h after stop of the ketamine infusion. The subjects will then be allowed to leave the trial site after successful completion of the discharge assessments (incl. C-SSRS; DSST, MOAA/S, CADSS, SFST), formal assessment and confirmation of their fitness. Discharge will be postponed if subjects fail to pass C-SSRS, DSST, MOAA/S, CADSS and/or SFST or any time if deemed necessary by the investigator (for details refer to Sections [5.2.5.2](#) and [5.2.5.5](#)).

For information regarding laboratory tests (including drug and virus screening), ECG, [REDACTED] C-SSRS, vital signs, safety tests (DSST, MOAA/S, CADSS, SFST), visual acuity test and physical examination incl. targeted examination, refer to Section [5.2](#).

For details on the trial procedures related to SARS-CoV-2/ COVID-19 in context of pandemic during screening period, refer to Appendix [10.7.3.1](#).

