		PGx sampling for CYP2C19 (blood)	For details, refer to Section 5.6.1 .
		Review Inclusion Exclusion Criteria (after results of Safety Laboratory, SARS CoV-2 PCR test and confirmation of CYP2C19 status are available)	If subject remains eligible based on above assessments, invite to Screening Ketamine Challenge (V2) that will be scheduled on a different day.

FLOW CHART C (SCREENING KETAMINE CHALLENGE)

Day -21 to -2 (Visit 2)

Planned time* [h:min]	Approximate clock time [hh:min]	Event(s)	Comment(s)
-12:00 ¹	20:00 ¹	Admission to trial site² Questioning for AEs and concomitant therapy Questioning for COVID-19 Body Temperature Drug Screening (urine) Alcohol Breath Test	¹ The time is approximate; admission is to be performed no later than 10 h prior to planned time 0:00. At discretion of the investigator or designee, admission on the next morning no later than 2 h prior to planned time 0:00 is possible. ² SARS-CoV-2 PCR test will be performed shortly (within 72 h) prior to admission
-2:00 ¹	06:00 ¹	Questioning for AEs and concomitant therapy C-SSRS 'since last visit' Targeted Physical Examination ² Vital Signs (BP, PR, SaO ₂) 12-lead ECG [REDACTED]	¹ the time is approximate; the procedures are to be performed and completed before light breakfast, within 2 h prior to PT 0:00 ² incl. skin inspection for signs of rash, check for lymphadenopathy and neurological examination
-0:30	07:30	Light breakfast	
0:00	08:00	240 mL fluid intake	
2:55	10:55	Light snack (clear liquid)	
3:00	11:00	240 mL fluid intake	
3:25	11:25	[REDACTED]	
	11:35	1 min break	
3:36	11:36	[REDACTED]	
	11:49	1 min break	
	11:50	[REDACTED]	
	11:55	[REDACTED]	
	12:00	1 min break	
	12:01	[REDACTED]	
	12:12	1 min break	
	12:13	[REDACTED]	
	12:19	1 min break	
4:20	12:20	CANTAB RVP	
	12:27	[REDACTED]	
	12:31	CANTAB SWM	
	12:37	[REDACTED]	
	12:41	CANTAB PAL Review In-/ Exclusion Criteria	in the end of PAL, eligibility results will be displayed
	12:53	2 min break	
4:55	12:55	Questioning for AEs Vital Signs (BP, PR, SaO ₂ +Resp.Rate/Effort) 12-lead ECG	instructing study subjects before ketamine infusion; [REDACTED]
4:59	12:59	[REDACTED]	[REDACTED]
5:00 ¹	13:00 ¹	Start of ketamine infusion¹ Start of continuous ECG and SaO ₂ monitoring	¹ if ketamine infusion is interrupted for a technical reason, the reason to be eliminated as soon as possible, before start of a new test, after the ongoing test has been completed (if applicable)
	13:03	[REDACTED]	[REDACTED] right before CANTAB RVP

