Proprietary confidential information © 2021 Boehringer Ingelheim International GmbH or one or more of its affiliated companies

		Vital Signs (BP, PR, SaO ₂) ¹	
5:06	13:06	CANTAB RVP	
	13:13	Vital Signs (BP, PR, SaO ₂) ¹	██████████ right before CANTAB SWM
	13:17	CANTAB SWM	
	13:23	Vital Signs (BP, PR, SaO ₂) ¹ PK blood (ketamine) ¹	██████████ right before CANTAB PAL
	13:27	CANTAB PAL Review In-/ Exclusion Criteria	in the end of PAL, eligibility results will be displayed
	13:39	Questioning for AEs Vital Signs (BP, PR, SaO ₂)	
5:40	13:40	██████████	
	13:53	Vital Signs (BP, PR, SaO ₂)	
	13:54	██████████	
	13:57	██████████	
	14:00	Vital Signs (BP, PR, SaO ₂) ██████████	
	14:01	██████████	
	14:12	Vital Signs (BP, PR, SaO ₂)	
	14:13	██████████	
	14:19	Questioning for AEs	
6:20	14:20	██████████	
6:30 ¹	14:30 ¹	Vital signs (BP, PR, SaO ₂) ██████████ Stop of ketamine infusion ¹ Stop of continuous ECG and SaO ₂ monitoring	¹ can be prolonged for a maximum of 15 min, in case delays from PT occur for CANTAB, ██████████ or terminated earlier, if the above tests are completed (or any test drops out)
6:45	14:45	Vital Signs (BP, PR, SaO ₂)	
7:00	15:00	Questioning for AEs Vital Signs (BP, PR, SaO ₂) 12-lead ECG	
7:15	15:15	Vital Signs (BP, PR, SaO ₂)	
7:30 ¹	15:30 ¹	Questioning for AEs Vital Signs (BP, PR, SaO ₂) Confirmation of recovery from ketamine ^{2,3} 240 mL fluid intake	¹ a minimum of 60 min of recovery follow up ² as per Criteria of recovery from ketamine ³ lunch will be served after confirmation of recovery
10:00	18:00	Questioning for AEs Vital Signs (BP, PR)	dinner will be served in the evening
24:00 ¹	08:00 ¹	Questioning for AEs Vital Signs (BP, PR) 12-lead ECG C-SSRS 'since last visit' DSST, MOAA/S, CADSS, SFST Targeted Physical Examination ² Discharge from trial site ^{3,4}	¹ Day -20 to -1 at V2. The time is approximate; the procedures to be performed and completed \pm 2 h. ² incl. skin inspection for signs of rash, check for lymphadenopathy and neurological examination ³ after confirmation of fitness by the investigator ⁴ breakfast will be served before discharge

* planned time 0:00 at *Screening Ketamine Challenge (V2)* should equal planned time 0:00 relative to *Drug administration (I)* on *Day 1 (V3, V4 and V5)*.

Proprietary confidential information © 2021 Boehringer Ingelheim International GmbH or one or more of its affiliated companies

FLOW CHART D (TREATMENT KETAMINE CHALLENGE)

Day 1 of each Treatment Period (Visits 3, 4 and 5)

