1.2.5 Residual Effect Period

The Residual Effect Period (REP) of ██████████, for lamotrigine 10 days, and for ketamine 24 hours. This is the period after the last dose with measurable drug levels and/or pharmacodynamic effects is still likely to be present.

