5 h after administration of *BI 425809 or placebo* and 2 hours after administration of *lamotrigine or BI 409306 or placebo*, ketamine infusion will start. Ketamine will be provided in vials containing 500 mg of ketamine hydrochloride in 10 ml solution for intravenous injection. Immediately prior to use, 10 ml of the solution from the vial will be aseptically transferred to 240 mL of Sodium Chloride (0.9%) Injection, USP (Normal Saline) and mixed well. The resultant solution will contain 2 mg of ketamine per ml. Ketamine infusion will be performed as a bolus of 0.26 mg/kg over 1 min, followed by continuous infusion of 0.0073 mg/kg/min over 89 min (reduced by 10% every 15 min). Infusion systems, e.g. B.Braun Vista Basic Infusion Pump or comparable, should be used for the i.v. administration of ketamine.

After ketamine infusion, recovery must be confirmed via criteria of recovery from ketamine as compared to pre-ketamine infusion. Recovery follow up can be terminated after a minimum of 60 minutes when all applicable criteria are met (see Section [5.2.5.6](#)).

Subjects will be kept under close medical surveillance until 24 h after the last study drug administration (i.e. *lamotrigine or BI 409306 or placebo*) in each treatment period, and overnight after ketamine infusion at screening. During ketamine infusion, vital signs including oxygen saturation will be measured frequently as per the [Flow Chart](#).

The treatments will be separated by a wash-out phase of at least 11 days.

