5.2 ASSESSMENT OF SAFETY

5.2.1 Physical examination, incl. targeted examination

At the screening examination (Visit 1), the medical examination will include demographics, height and body weight, smoking and alcohol history, relevant medical history and concomitant therapy, visual acuity test, C-SSRS assessment, safety testing (DSST, MOAA/S, CADSS and SFST), review of vital signs (BP and PR incl. orthostatic testing, SaO₂), 12-lead ECG, [REDACTED] laboratory tests, and a physical examination.

At the screening ketamine challenge (Visit 2) and during the treatment periods (Visits 3, 4 and 5), vital signs (BP, PR, SaO₂), 12-lead ECG, continuous ECG monitoring, laboratory tests, and a physical examination with a targeted examination (skin inspection for signs of rash, check for lymphadenopathy and neurological examination (mental status, motor examination, reflexes, sensory, gait and cranial nerves)) will be performed at the time points indicated in the [Flow Chart](#). *Each time at discharge from trial site,* the subjects will be assessed by an investigator for their fitness including C-SSRS assessment, safety testing (DSST, MOAA/S, CADSS and SFST), review of vital signs (BP, PR, SaO₂), 12-lead ECG, laboratory tests, a physical examination with a targeted examination as described above.

At the end of trial examination (Visit 6), the medical examination will include review of vital signs (BP, PR, SaO₂), 12-lead ECG, laboratory tests, C-SSRS assessment, visual acuity test, a physical examination with a targeted examination as described above and determination of weight.

In context of pandemic, evaluation of subjects for COVID-19 will be performed ***at each visit***, including temperature assessment, questionnaire and medical assessment, and PCR test for SARS-CoV-2. For details, refer to Appendix [10.7](#).

Results of the physical examinations incl. targeted examinations and evaluation of subjects for COVID-19 will be kept in source data only, but not collected in the CRF. Only clinically relevant abnormal findings will be reported as AEs.

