6. GENERAL ANALYSIS DEFINITIONS

6.1 TREATMENTS

For basic study information on treatments to be administered, assignment of treatment groups, and selection of doses, cf. Section 4 of the CTP.

Each subject is planned to be treated in three subsequent treatment periods with one single dose at Day 1 in each treatment period:

- Test treatment 1 (T1):
300 mg of Lamotrigine as tablet
- Test treatment 2 (T2):
[REDACTED] of BI 409306 as film-coated tablet
- Test treatment 3 (T3):
[REDACTED] of BI 425809 as film-coated tablet
- Reference treatment (R):
Placebo as film-coated tablet

Each subject is planned to be randomly allocated to one of 18 3-period sequences including placebo in one of the periods and 2 out of 3 active treatments in the remaining periods:

T1–T2–R, T1–R–T2, T1–T3–R, T1–R–T3, T2–T1–R, T2–R–T1, T2–T3–R, T2–R–T3, T3–R–T1, T3–T1–R, T3–T2–R, T3–R–T2, R–T1–T2, R–T2–T1, R–T1–T3, R–T3–T1, R–T2–T3, R–T3–T2.

Each treatment period is separated by a washout period of at least 11 days.

[REDACTED] : *The Residual Effect Period (REP)* [REDACTED]
[REDACTED], for lamotrigine 10 days, and for ketamine 24 hours. This is the period
after the last dose with measurable drug levels and/or pharmacodynamic effects is still likely
to be present.

For statistical analyses of AEs and vital signs, the following separate analysis phases will be defined for each subject:

Table 6.1: 1 Analysis phases for statistical analysis of AEs and actual treatment for analysis of vital signs

Study analysis phase	Label of analysing treatment	Label of actual treatment	Start	End
Screening	Screening	Screening	Date of informed consent	Start date/time of screening ketamine infusion
		Screening+Ketamine	Start date/time of screening ketamine infusion	End date/time of screening ketamine infusion + 24 h
		Screening	End date/time of screening ketamine infusion + 24 h	Start date/time of first administration of study treatment (Planned time: 00:00h) in the respective treatment period
On treatment ^{1, 2, 3}	Placebo, [REDACTED] BI 409306, BI 425809 or 300mg Lamotrigine, respectively	Placebo, [REDACTED] BI 409306, BI 425809 or 300mg Lamotrigine, respectively	Start date/time of administration of the first study treatment (Planned time: 00:00h) in the respective treatment period	Start date/time of on-treatment ketamine infusion or 12:00 a.m. on day after subject's trial completion date, whatever comes first

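### Section 6.2.1 permits release 5 h after the screening ketamine infusion, while Section 4.1.4 and Flow Charts A and C require an overnight stay with discharge next morning

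*Protocol*

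**What the plan says.** Four parts of the protocol govern how long a subject stays after the Visit 2 infusion.

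- **Section 6.2.1** has subjects "kept under close medical surveillance for at least 5 h after stop of the ketamine infusion". They may then leave after passing the discharge assessments (C-SSRS, DSST, MOAA/S, CADSS, SFST) and having their fitness confirmed. Discharge is postponed if a test is failed or if the investigator thinks it necessary.
- **Section 4.1.4** requires close medical surveillance until 24 h after the last study drug dose "in each treatment period, and overnight after ketamine infusion at screening".
- **Flow Charts A and C** place the Visit 2 discharge, with its checks, at planned time 24:00, clock time 08:00. The note to that row in Flow Chart C reads "Day -20 to -1 at V2. The time is approximate" and gives ±2 h. The challenge itself is on Day -21 to -2, so this is the following day.
- **Section 6.1** allows ±2 h on all days for "C-SSRS assessments, targeted physical examination, safety tests (DSST, MOAA/S, CADSS and SFST) and laboratory tests".

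Section 5.2.1 adds that at each discharge "the subjects will be assessed by an investigator for their fitness including C-SSRS assessment", together with safety tests, vital signs, ECG, laboratory tests and examination.

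Two other places bear on the 24 h after ketamine. Section 1.2.5 gives residual effect periods "for lamotrigine 10 days, and for ketamine 24 hours". In SAP Section 6.1, Table 6.1: 1, the Screening+Ketamine label runs until "End date/time of screening ketamine infusion + 24 h".

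**The concern.** The same infusion has two release rules. A site that reads Section 6.2.1 as its instruction for Visit 2 can send a subject home the same evening. It would then breach Section 4.1.4, both flow charts and the Section 6.1 window.

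Visit 2 is the subject's first ketamine exposure in the trial, so nothing is yet known of his individual response to it. An early release would end observation that evening. It would also remove the scheduled next-morning contact: in Flow Chart C the only AE questioning after 18:00 is in the 24:00 row. The flow charts list phone follow-up only within the treatment periods, so the next listed contact would be admission for Visit 3.

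What is at stake is subject safety and uniform conduct across the two sites, not the efficacy analysis.

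**Working it through.** **Inputs**

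- Planned time 0:00 is 08:00 (Flow Charts A and C).
- Planned infusion stop is 6:30, so 08:00 + 6.5 h = 14:30, as the charts print.
- Planned discharge is 24:00, so 08:00 + 24 h = 08:00 next day, as the charts print.
- Minimum stay after stop is 5 h (Section 6.2.1).
- The window for the discharge checks is ±2 h (Flow Chart C, Section 6.1), that is 06:00 to 10:00.
- The infusion may be prolonged by up to 15 min (Flow Chart C).
- The residual effect period of ketamine is 24 h (Section 1.2.5).

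**Release under Section 6.2.1**

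14:30 + 5 h = 19:30. This is half an hour after the 19:00 dinner in Flow Chart A, so it is a workable time to leave.

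**Comparison with the flow charts**

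| Quantity | Calculation | Section 6.2.1 minimum | Flow Charts A and C |
|---|---|---|---|
| Earliest or planned release | as above | 19:30 same day | 08:00 next day |
| Observation after stop | release − 14:30 | 5 h | 17.5 h (15.5 to 19.5 h with ±2 h) |
| Part of the 24 h period off site | 24 − observation | 19 h | 6.5 h |
| Share of the 24 h period on site | observation / 24 | 5/24 = 21% | 17.5/24 = 73% |

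Timing of the discharge checks if done at 19:30:

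- before planned time: 19:30 to 08:00 = 12.5 h;
- before the window opens: 19:30 to 06:00 = 10.5 h.

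**Sensitivity to the infusion stop**

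With a 15 min prolongation, stop is 14:45, earliest release is 19:45, and the gap to 08:00 is 12.25 h. If the infusion ends early because the assessments are complete (Sections 4.1.2 and 6.1), release could come before 19:30 and the gap would be longer. So 19:30 is a nominal time, not a lower bound.

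**Is 5 h a release threshold or only a floor?**

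Section 6.2.2 uses the same construction for the treatment periods: surveillance for at least 24 h after dosing, after which subjects may leave once the discharge assessments are passed. There the stated minimum is clearly the point at which release becomes permissible. Read the same way, the 5 h in Section 6.2.1 is the release threshold for Visit 2. Its postponement clause covers only failed tests and investigator judgment, so it does not bring back an overnight stay for a subject who passes.

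**The case against.** The strongest reply is that the rest of the protocol already settles the matter. The 5 h is a minimum. Release depends on the discharge assessments, and for Visit 2 these are scheduled only at 24:00, ±2 h. Section 6.2.1 refers to Section 5.2 for most of these measurements, and Section 5.2 sends the timing of the C-SSRS, targeted examination, vital signs and ECG to the flow chart. Section 4.2.2.2 also has Visit 2 follow the schedule of the treatment days. On this reading an overnight stay is the only course that satisfies every section.

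That last point stands, and it shows which rule was intended. It does not remove the conflict. Section 5.2.5.5 ties the DSST, MOAA/S, CADSS and SFST to discharge rather than to a clock time, and no text ranks the flow charts above Section 6.2.1. A site can follow the sentence exactly and still break the schedule.

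Three further points on the other side are fair.

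- The residual effect period describes likely drug effect; it is not a required in-house stay. Discharge at 08:00 also leaves 6.5 h of it off site. The 21% and 73% describe coverage, not harm.
- The SAP label attributes events and vital signs; it does not require on-site observation. AE summary tables cover the on-treatment phase only, so screening events are listed rather than summarised. AEs are collected from consent to end of trial wherever the subject is.
- Nothing in the documents indicates that a site has released, or would release, a subject early.

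These limit the consequence. They do not make the two rules agree.

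**Conclusion.** The point holds. Section 6.2.1 contradicts Section 4.1.4 and Flow Charts A and C on the stay after the screening infusion. If a site followed it, observation after stop would fall from 17.5 h to 5 h at planned times, and the next-morning assessment would be lost.

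This rests on the planned stop at 14:30 and on a site giving the Section 6.2.1 sentence priority over the charts. Recovery from ketamine would still be confirmed under Section 5.2.5.6, and the discharge checks would still be done, outside their window. The primary endpoint, the on-ketamine baseline and the sample size are unaffected.

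This is an inconsistency between sections. It should be corrected because the more permissive rule concerns subject safety.

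**What to change.** In Section 6.2.1, replace the 5 h sentence with wording to this effect: subjects stay under close medical surveillance overnight after the ketamine infusion and may leave after the planned-time 24:00 assessments (08:00 next day, ±2 h) and confirmation of fitness, as in Section 4.1.4 and Flow Charts A and C. Keep the sentence on postponing discharge.

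In the same edit, complete the arrival sentence, which mentions only morning arrival. Flow Chart C has evening admission as the default and adds that, at the investigator's or designee's discretion, "admission on the next morning no later than 2 h prior to planned time 0:00 is possible".

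The cost is wording in one section. The overnight stay and the 24:00 assessments are already in the protocol, so no procedure is added.
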